9.6 STATISTICAL METHODS AND DETERMINATION OF SAMPLE SIZE

9.7.1 SAMPLE SIZE

It is estimated that 320 prospects will need to be screened in order to have 40 per group for a total of 160 participants.

9.7.2 ANALYSIS POPULATIONS

1. **Safety Population:** will include all randomized subjects who meet eligibility criteria and meet with their treatment provider for session 1.

2. **Intent-to-Treat Population:** will include all subjects who meet with their treatment provider for session 1 and for whom the treatment provider determines the subject meets diagnostic criteria for 780.52 Insomnia Disorder.
3. **Pre-Protocol (PP) Population:** will include all subjects who complete the 6 sessions of treatment as well as the 3 month, 6 month and 12 month follow up assessment. It is estimated that 80% of those who complete session 1 will complete session 6. It is estimated that 80% of those who complete session 6 will complete the 3 month, 6 month and 12 month follow up assessments. This will result in 25 participants who will have completed the entire study.

9.7.3 SAFETY PARAMETERS

Safety parameters comprise the C-SSRS.

The number and percentage of patients with suicidal ideation or suicidal behavior as recorded on the C-SSRS will be summarized by treatment group. The distribution of responses for most severe suicidal ideation and most severe suicidal behavior during the patient's lifetime, during the treatment period, and during the safety follow-up period will also be presented by treatment group for the Safety Population. Supportive listings will be provided and will include the "Participant Number" (PN), lifetime history, and post baseline values. Intensity of suicidal ideation, suicidal behavior type, and lethality of suicidal behavior will also be included in these listings. A listing of all AEs occurring in patients who have suicidal ideation or suicidal behavior will also be provided.

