- 1) Lower the threshold for seizures in persons with epilepsy;
- 2) Precipitate mania in bipolar participants;
- 3) Exacerbate parasomnias;
- 4) Prevent adequate ventilation in patients with obstructive sleep apnea; and/or
- 5) Aggravate the day time somnolence to the point where it is no longer safe for the participant to drive, operate machinery and/or make judgments that adequately promote their own and/or the safety and well-being of others.

The risk is generally higher when these illnesses are untreated. Prospective participants treated for any of these illnesses and interested in participating must have the written approval of their treatment provider in order to be eligible. Prospective participants will be screened and informed of these potential risks. If any of these risks (1-5 above) occur during the study, the participant will be asked to immediately discontinue the sleep restriction, and an alternative treatment not involving sleep restriction will be offered. The participant will also have the option of discontinuing the treatment if they prefer this to proceeding with the alternative treatment which does not involve sleep restriction.

SAMPLE SIZE

It is estimated that 320 prospects will need to be screened in order to have 40 per group for a total of 160 participants.

ANALYSIS POPULATIONS

Safety Population: will include all randomized subjects who meet eligibility criteria and meet with their treatment provider for session 1.

Intent-to-Treat Population: will include all subjects who meet with their treatment provider for session 1 and for whom the treatment provider determines the subject meets diagnostic criteria for 780.52 Insomnia Disorder.

Pre-Protocol (PP) Population: will include all subjects who complete the 6 sessions of treatment as well as the 3 month, 6 month and 12 month follow up assessment. It is estimated that 80% of those who complete session 1 will complete session 6. It is estimated that 80% of those who complete session 6 will complete the 3 month, 6 month and 12 month follow up assessments. This will result in 25 participants who will have completed the entire study.

HYPOTHESES

Hypothesis 1: Treatment Effect on Subjective Measures from Weekly Sleep Log

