complete 12 month follow-up. These subjects will then be eliminated as relates to analyses involving 12 month follow-up data. Statistical analyses will be conducted to determine whether those with missing data differ significantly from those without missing data using t test comparing the two groups on total scores on Insomnia Severity Index at pre-treatment as well as post-treatment.

STATISTICS

Repeated measures analysis of variance (2 X 4 ANOVA) will be used to test the Hypotheses 1-3, 5-10 and 11-16. Any statistically significant ANOVAs will be followed by pairwise t-test comparisons to identify between group differences. Chi square will be used to test Hypotheses 4 and 11.

SAFETY ANALYSIS

In general the potential risks for participants are minimal. The treatment approaches involved in related studies have been shown to be a safe procedure and in most of the published studies people who underwent these procedures did not report any harmful effects.

Prospective participants will be informed that it is nonetheless possible you may experience some discomforts during the treatment. These may include temporary decrease in time asleep and accompanying daytime drowsiness. Some people may become anxious while initially following the treatment procedures, with increased worry about their sleep difficulty. Anxiety and worry about sleep difficulty are in fact common among persons with insomnia. Therefore identifying and addressing these possibilities will be directly addressed during the treatment, and participants will be given guidance about what to expect and how to manage should these discomforts occur. Prospective participants will also be informed that persons with certain medical illnesses, certain psychiatric illnesses or other sleep disorders may be at increased potential risk of exacerbation of that illness. This is a possibility for participants with epilepsy, bipolar depression, parasomnia, obstructive sleep apnea or other illnesses which have excessive daytime sleepiness as a feature of the parent disorder. The participant may (or may not) be assigned to a treatment which involves sleep restriction. Sleep loss through sleep restriction may

- 1) Lower the threshold for seizures in persons with epilepsy;
- 2) Precipitate mania in bipolar participants;
- 3) Exacerbate parasomnias;
- 4) Prevent adequate ventilation in patients with obstructive sleep apnea; and/or

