9.5.2.2 CAUSALITY ASSESSMENT

The causality assessment must be recorded on the appropriate AE reporting page of the patient's eCRF. Causal relationship must be assessed by answering the following question:

Is there a reasonable possibility the **sleep study treatment** caused the event?

Yes: **There is evidence to suggest a causal relationship between the sleep study treatment and AE, i.e.:**

1. There is a reasonable temporal relationship between the IP and the event, and/or
2. The event is unlikely to be attributed to underlying/concurrent disease or other factors, and/or
3. Positive de-challenge and/or re-challenge exist

No: **There is no evidence to suggest a causal relationship between the sleep study treatment and AE, i.e.:**

1. There is no reasonable temporal relationship between the IP and the event, or
2. The patient did not take the IP, or
3. The event is likely to be attributed to underlying/concurrent disease or other factors, or
4. The event is commonly occurring in the (study) population independent of IP exposure

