9.5.2.5 REPORTING ADVERSE EVENTS AND SERIOUS ADVERSE EVENTS

At each visit, patients are to be queried regarding any AEs or SAEs that have occurred since the previous visit. Patients will be asked to volunteer information with a non leading question such as, —How do you feel since your last visit?“ Study center personnel will record all pertinent information in the patient’s eCRF. All AEs must be recorded on the appropriate AE reporting page of the patient’s eCRF whether or not they are considered causally related to the sleep study treatment..

For every AE, the Investigator must:

1. Provide an assessment of the seriousness of the event (ie, is it an SAE?), as well as the severity and causal relationship
2. Document all actions taken with regard to the IP
3. Detail any other treatment measures taken for the AE
4. Document the outcome of the AE

In addition, patients are to be reminded, as described in the ICF and in accordance with Section 9.5.2.1, to notify study center personnel of any AEs occurring during the 30-day poststudy period. Any AEs reported by the patient (or patient representative) during this period are to be recorded in original source documents. AEs are also to be recorded in the eCRF if at least one of the following conditions is met: 1) the event meets the criteria for an SAE (see Sections 9.5.2.4 and 9.5.2.5), and/or 3) the event is judged by the Investigator to be potentially causally related to sleep study treatment.

Any AEs that are ongoing at the time of the final protocol-defined study visit will be followed until the condition returns to pre-study status, has resolved or stabilized, or can be explained as being unrelated to the sleep study treatment. If a follow-up visit is deemed necessary for appropriate safety surveillance, it will take place within 30 days of the final protocol-defined study visit.

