9.5.3.2 Visit 2 (or Baseline Visit)

The Baseline Visit 2 will be conducted up to 14 days after Screening (Visit 1) to determine whether the patient is eligible to continue into the randomization, open label, sleep hygiene controlled 6 week study treatment period.

At the visit 2, the following procedures will be performed:

1. Review of all inclusion/exclusion criteria
2. Administer SRSM (Self Report Sleep Measures)
3. Administer CGI-S (Clinical Global Impression –Severity Scale)
4. Administer CGI (Clinical Global Impression)
5. Administer C-SSRS (Columbia-*Suicide* Severity Rating Scale)
6. Review and record AEs
7. Eligible patients will be assigned an “Participant Number” (PN).

Administer Randomization (must occur after all efficacy and safety assessments)

Schedule Visit 3

9.5.3.3 Visit 3

At Visit 3, the following procedures will be performed:

1. Review of all inclusion/exclusion criteria
2. Administer SRSM (Self Report Sleep Measures)
3. Administer CGI-S (Clinical Global Impression –Severity Scale)
4. Administer CGI (Clinical Global Impression)
5. Administer C-SSRS (Columbia-*Suicide* Severity Rating Scale)
6. Review concomitant medications

Schedule Visit 4

9.5.3.4 Visit 4

At Visit 4, the following procedures will be performed:

1. Review of all inclusion/exclusion criteria
2. Administer SRSM (Self Report Sleep Measures)
3. Administer CGI-S (Clinical Global Impression –Severity Scale)
4. Administer CGI (Clinical Global Impression)
5. Administer C-SSRS (Columbia-*Suicide* Severity Rating Scale)
6. Review concomitant medications

Schedule Visit 5

9.5.3.5

Visit 5

At Visit 5, the following procedures will be performed:

1. Review of all inclusion/exclusion criteria
2. Administer SRSM (Self Report Sleep Measures)
3. Administer CGI-S (Clinical Global Impression –Severity Scale)
4. Administer CGI (Clinical Global Impression)
5. Administer C-SSRS (Columbia-Suicide Severity Rating Scale)
6. Review concomitant medications

Schedule Visit 6

9.5.3.6

Visit 6

At Visit 6, the following procedures will be performed:

1. Review of all inclusion/exclusion criteria
2. Administer SRSM (Self Report Sleep Measures)
3. Administer CGI-S (Clinical Global Impression –Severity Scale)
4. Administer CGI (Clinical Global Impression)
5. Administer C-SSRS (Columbia-Suicide Severity Rating Scale)
6. Review concomitant medications

Schedule Visit 7

9.5.3.7

Visit 7

At Visit 7, the following procedures will be performed:

1. Review of all inclusion/exclusion criteria

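### Section 9.7.3 defines safety as the C-SSRS alone, so the protocol plans no by-arm summary of AEs, SAEs or the five sleep-restriction risks it names

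*Protocol*

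**What the plan says.** Section 9.7.3 of the protocol opens with "Safety parameters comprise the C-SSRS". It then sets out the output: "The number and percentage of patients with suicidal ideation or suicidal behavior as recorded on the C-SSRS will be summarized by treatment group", with distributions of the most severe ideation and behavior by treatment group and supporting listings. AEs enter once: "A listing of all AEs occurring in patients who have suicidal ideation or suicidal behavior will also be provided".

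Section 8.0 (Safety and Tolerability End Points, and again under Safety Analysis) describes the harms expected. Of the milder discomforts it says "These may include temporary decrease in time asleep and accompanying daytime drowsiness". It then numbers five risks of sleep restriction: a lowered seizure threshold, mania, worse parasomnias, inadequate ventilation in sleep apnea and, fifth, "Aggravate the day time somnolence to the point where it is no longer safe for the participant to drive". It also says that a participant may or may not be assigned to a treatment with sleep restriction, and that sleep restriction is to stop if one of the five occurs.

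On collection, section 9.5.2.5 says "At each visit, patients are to be queried regarding any AEs or SAEs that have occurred since the previous visit", with all AEs recorded on the eCRF whether or not they are considered related. Among the visit-by-visit procedures in section 9.5.3, "Review and record AEs" stands only in the Visit 2 list.

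**The concern.** The protocol identifies harms tied to one treatment component, expects that component in some arms and not others, and collects AEs. It then defines its safety parameters so that none of this reaches a by-arm table. An analysis plan that followed section 9.7.3 would report suicidality by arm and nothing on daytime somnolence, which is the harm most closely linked to sleep restriction in the protocol's own text. The Introduction cites daytime sleepiness as a reason some patients leave CBT-I. The trial could then report the relative benefit of four behavioral treatments without the matching account of harm.

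Two drafting faults weaken the data that such tables would use. The visit lists do not carry AE review beyond Visit 2, and the causality criteria still contain drug-trial wording about an IP that no participant receives.

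**Working it through.** The protocol states no figure for a safety comparison, so there is nothing to reproduce. The check is mainly a comparison of sections.

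**1. Planned safety output against named harms**

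- C-SSRS ideation and behavior: by-arm summary planned (9.7.3).
- AEs in patients with suicidal ideation or behavior: a listing only, no by-arm table (9.7.3).
- AEs in all other patients: no output planned.
- SAEs: no output planned beyond that same listing.
- The five numbered sleep-restriction risks: 0 of 5 have a by-arm summary.
- Discontinuation of sleep restriction because of one of the five: no count planned.

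The part of section 8.0 headed Safety Analysis repeats the risks and the management step but contains no analysis. None of Hypotheses 1 to 16 has AEs, somnolence or stopping of sleep restriction as an outcome. The nearest is Hypothesis 1c, which compares total sleep time after treatment as an efficacy measure. It would miss a temporary loss of sleep during treatment and the drowsiness that goes with it.

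**2. Collection**

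Section 9.5.2.5 requires an AE query at each visit. The lists for Visits 3 to 11 omit it, and the Schedule of Evaluations has no AE row. At Visit 2, randomization comes after all assessments. Session 1 takes place at that visit (9.4.6) and is identical in all four arms. The one listed AE review therefore falls before the arms have diverged.

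**3. Causality wording (9.5.2.2)**

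The question asked, and the Yes and No headings, refer to the sleep study treatment. The No criteria are joined by or, and one is "The patient did not take the IP, or". No arm has an IP, so everyone meets it. The Yes criteria are joined by and/or, and one of them (the event is unlikely to be due to underlying disease or other factors) does not mention IP. One event can therefore satisfy Yes and No together. IP wording also remains in 9.5.2.1, 9.5.2.4 and 9.5.2.5.

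**4. Illustration of size (rates assumed)**

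Inputs: 40 per arm (9.7.1). Two arms, CBT-I and Combined, are taken to include sleep restriction, giving 2 × 40 = 80. The split is inferred from the Introduction's description of CBT-I, since the session scripts are in separate folders (9.4.3).

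Chance of at least one event in n participants = 1 − (1 − p)^n:

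- p = 1%: 1 − 0.99^80 = 0.552
- p = 2%: 1 − 0.98^80 = 0.801
- p = 5%: 1 − 0.95^80 = 0.983

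Power of a by-arm comparison (two-sided alpha 0.05, also assumed) = Φ{[|p2 − p1| − 1.96√(2p̄(1 − p̄)/n)] / √([p1(1 − p1) + p2(1 − p2)]/n)}, where p̄ is the mean of p1 and p2. For 10% v 30%:

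- n = 40 per group: (0.20 − 1.96 × 0.0894)/0.0866 = 0.285, power 0.61
- n = 80 per group (two arms pooled against two): (0.20 − 1.96 × 0.0632)/0.0612 = 1.24, power 0.89

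For 5% v 15% the same formula gives 0.32 and 0.56. Tables by arm would be informative for a large difference in somnolence. Rarer harms could only be described.

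**The case against.** The strongest reply is that the gap need not survive into the report. AEs are recorded on eCRFs with known assignment, an independent DSMB reviews safety data under a charter (9.8), an integrated clinical and statistical report is promised (10.2), and AE tables are often specified in an analysis plan, which is not at hand. This stands in part. A reader might infer that harms will never be compared, or that the trial cannot say which arm is less safe. The documents do not support that; they support only that this protocol plans no such comparison. The reply does not remove the point, because 9.7.3 is not silent: it says what the safety parameters are, and AEs are not among them.

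Four other inferences also go too far.

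- **That AEs go uncollected after Visit 2.** Section 9.5.2.5 still requires the query at each visit, and section 9.5.2 requires a documented evaluation at every visit. The visit lists are inconsistent with this but do not cancel it.
- **That the causality rule makes every event unrelated.** The question concerns the sleep study treatment, and a Yes criterion without IP remains open. The rule contradicts itself; it does not force No.
- **That AEs in suicidal patients are tabulated by arm.** The protocol plans only a listing for them.
- **That at least one named event is close to certain.** Assumed rates of 3% to 5% in 80 would give 91% to 98%, but the documents supply no rate. The exclusions in 9.3.2 (seizure history, sleep apnea above the cutoff, unstable psychiatric illness) make lower rates plausible for several of the five. Nor does the chance of one event measure a lost comparison.

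**Conclusion.** The point holds as a conflict between what the protocol collects and warns of and what it says it will summarise. Its size is a count of outputs: none of the five named risks, and no AE or SAE, has a planned by-arm summary. That rests on the text alone and needs no event rate. The illustrative figures depend on assumed rates, an assumed alpha and an inferred split of arms; they show only that tables by arm would be useful for somnolence and descriptive for the rest. The visit-list and IP faults are secondary inconsistencies that should be corrected with it. The change should be made, though the data to repair the gap are already meant to be collected.

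**What to change.** 1. In 9.7.3, state that the safety parameters are AEs, SAEs, the five sleep-restriction risks named in section 8.0 (together with discontinuations of sleep restriction) and the C-SSRS. Each is to be summarised as counts and percentages by arm in the Safety Population, with rare events described and not tested.
2. Reconcile the Visit 3 to 11 lists in 9.5.3 and the Schedule of Evaluations with the each-visit AE query in 9.5.2.5.
3. Replace the leftover IP wording in 9.5.2.1, 9.5.2.2, 9.5.2.4 and 9.5.2.5 with sleep study treatment, adapting the phrases about doses and dependency, so that the Yes and No causality criteria no longer both apply to one event by default.

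The cost is a few tables from data the protocol already requires, a line in each visit list, a row in the schedule and corrected wording. No treatment or clinical rule changes.

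### Section 9.7.3 sets the safety parameters as the C-SSRS alone, so adverse events collected at every visit have no planned summary by treatment arm

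*Protocol*

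**What the plan says.** **Analysis.** Protocol Section 9.7.3 opens with "Safety parameters comprise the C-SSRS". It then plans by-arm counts and percentages of patients with suicidal ideation or behavior, by-arm distributions of the most severe ideation and behavior, and supporting C-SSRS listings. Its one mention of adverse events comes last: "A listing of all AEs occurring in patients who have suicidal ideation or suicidal behavior will also be provided".

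**Collection.** Sections 9.5.2.1 to 9.5.2.4 define adverse events and serious adverse events and set out the causality and severity assessments. Section 9.5.2.5 adds: "At each visit, patients are to be queried regarding any AEs or SAEs that have occurred since the previous visit". It requires every event to be recorded, whether or not it is thought related to treatment.

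**Expected harm.** Section 8.0, under Safety and Tolerability End Points and again under Safety Analysis, says of the discomforts of treatment: "These may include temporary decrease in time asleep and accompanying daytime drowsiness". Among the risks of sleep restriction in people with certain illnesses it gives: "Aggravate the day time somnolence to the point where it is no longer safe for the participant to drive". It notes that a participant may or may not be assigned to a treatment that uses sleep restriction. If a listed risk occurs, sleep restriction is to stop and an alternative is to be offered.

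**Visit lists.** Only Section 9.5.3.2 (Visit 2) contains "Review and record AEs". The same section ends with "Administer Randomization (must occur after all efficacy and safety assessments".

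**The concern.** The trial compares four behavioral treatments. The harm the protocol expects depends on which one a participant is given. The introduction describes sleep restriction as a usual component of CBT-I and reports that the resulting daytime sleepiness leads some patients to drop out. A reader of the final report would want to know whether sleepiness was more frequent in the arms that use sleep restriction.

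Under Section 9.7.3 that question has no planned answer. The protocol collects and grades the events, then defines a safety analysis that leaves them out unless the patient also has a positive C-SSRS. Because a listed event can end sleep restriction for that participant, these events also bear on which treatment was actually received. A table added after the data are seen, in an open-label trial, carries less weight than one that was planned.

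**Working it through.** The plan states no figure on this point, so the check sets the sections side by side.

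1. **Is a by-arm adverse event summary planned anywhere?**
   - Section 9.7.3: all by-arm output concerns suicidal ideation or behavior. The adverse event output is a listing, restricted to patients with either.
   - Section 8.0, Safety Analysis: despite its heading, this gives the risk narrative and the action to take if a risk occurs. It specifies no tabulation.
   - Section 8.0, Hypotheses 1 to 16: these cover sleep measures, insomnia severity and diagnosis, satisfaction, distress, impairment and opinion of treatment. None concerns an adverse event.
   - Sections 9.5.2.1 to 9.5.2.5: collection, grading and follow-up of individual cases only.
   - Section 9.8: the data and safety monitoring board reviews safety data, but its analyses are left to its charter.

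   By-arm adverse event summaries planned: 0.

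2. **Do the safety sections agree on what safety means?** The Safety and Tolerability End Points in Section 8.0 are reduced sleep, drowsiness, anxiety and the five sleep-restriction risks. They do not mention the C-SSRS. Section 9.7.3 names the C-SSRS and none of those. The two sections have no item in common.

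3. **Would the restricted listing catch the named harm by accident?** Only for a participant who has both the sleepiness event and suicidal ideation or behavior. A participant with marked sleepiness and a negative C-SSRS appears in no planned safety output.

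4. **Do the data exist to fill the gap?** Yes. Section 9.5.2.5 requires the query at each visit and the recording of every event. Section 9.7.2 already defines a Safety Population.

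5. **Do the visit lists match Section 9.5.2.5?** Sections 9.5.3.1 to 9.5.3.11 hold 11 visit lists. Adverse event review is named in 1 of them, Visit 2, where randomization follows all assessments. The lists for Visits 3 to 11 (11 − 2 = 9 lists), which cover the time after randomization, do not name it.

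**The case against.** **The analysis plan may supply the tables.** This is the strongest objection. Section 9.7.3 does not say that only the C-SSRS will be analyzed, and its adverse event listing can be read as a supporting output for the C-SSRS rather than a limit on reporting. Adverse event tables are commonly left to a statistical analysis plan, and one may exist. Had Section 9.7.3 been silent, that would settle the matter. But it states what the safety parameters consist of and for whom events are listed. An analysis plan that follows it has no by-arm event table, and one that adds the table departs from the protocol. The objection limits the size of the point but does not remove it.

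**Participants are protected anyway.** This stands. Individual events are followed up, sleep restriction is stopped when a listed risk occurs, and the board reviews safety data. The gap is in planned analysis and reporting.

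**The table would be imperfect.** This also stands. Events are elicited by one non-leading question in an open-label trial, so sleepiness may be under-reported or reported unevenly across arms. The summary should therefore be descriptive.

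Two stronger readings are tempting and are not supported:

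- A reader might infer from the visit lists that adverse events go unasked after randomization. Section 9.5.2.5 requires the query at every visit, and Section 9.5.2 requires a documented evaluation at each. The lists are a drafting mismatch.
- A reader might infer that the weekly sleep logs are wrongly left out of the safety analysis. Section 8.0 says "Repeated measures analysis of variance (2 X 4 ANOVA) will be used to test the Hypotheses 1-3, 5-10 and 11-16", and Hypotheses 1 and 8 compare the log data before treatment with after treatment or at 12 months. An early fall in total sleep time that later recovers would not show there. But that is a legitimate choice of endpoint. The introduction says CBT-I deliberately manipulates total sleep time, so an early fall partly shows that the treatment was delivered. Week-by-week descriptive tables are ordinary analysis-plan content, and the protocol does not exclude them.

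**Conclusion.** The point holds in a narrow form. Section 9.7.3 fixes the safety parameters too tightly. Adverse events that the protocol requires to be collected and graded, including the sleepiness it names as a risk, have no planned summary by arm.

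The severity is minor. No error rate, sample size or efficacy conclusion is affected, and the data could still be tabulated later, though not as a planned analysis.

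The conclusion rests on reading the opening sentence of Section 9.7.3 as defining the full set of safety parameters, which is its plain sense. It also assumes that the arms differ in their use of sleep restriction. Section 8.0 implies this, but the session scripts are held in separate files and are not in the protocol.

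**What to change.** 1. Change the opening of Section 9.7.3 to: *Safety parameters comprise adverse events and the C-SSRS.*
2. Add to that section, for the Safety Population, a descriptive summary by treatment arm of all AEs and SAEs by severity and causality, with daytime sleepiness or somnolence shown on its own line. No hypothesis test is needed.
3. Keep the existing listing for patients with suicidal ideation or behavior as a supporting output.
4. Add adverse event review to the Visit 3 to 11 lists in Section 9.5.3, so that they agree with Section 9.5.2.5.

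A by-arm table of total sleep time from the Weekly Sleep Log at each treatment week is an optional descriptive addition. It should not be classed as a safety parameter, and its absence is not an error.

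The cost is a few descriptive tables from data already planned for collection and one line in each of nine visit lists. No visit or measurement is added.
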